- HTLS Diet: 55% total CHO (85% complex / 15% simple CHO), 30% fat, 15% protein
- LTHS Diet: 35% total CHO (½ complex / ½ simple CHO), 50% fat, 15% protein
- LTLS Diet: 35% total CHO (85% complex / 15% simple CHO), 50% fat, 15% protein

Power Analysis and Sample Size: Our primary outcome is a continuous variable, percent time pH < 4.0 in the 24hr period. This is based on the clinical gold standard of pH < 4.0 for > 5.5% of the 24hr period. To determine sample size, we used data from 205 obese patients with chronic GERD from [name] clinic population. In this sample, the SD for percent time < pH was 9.8 and the interclass correlation was 0.39 ($\omega = \omega^2_b / (\omega^2_b + \omega^2_e)$). We used these values as inputs into a statistical simulation (10,000 replications) to determine the probability of detecting any treatment group effect using the linear mixed effects model. The following table presents the power of an overall (4 d.f.) test to detect various absolute changes in pH by diet groups ($\omega_1, \omega_2, \omega_3, \omega_4$). We assume $n_1=40$ subjects per group complete the entire study and $n_2=5$ or $n_2=3$ subjects per group complete 80% of the study before returning for pH testing. We use a two-sided significance level of 0.05.

Absolute effect size	3.7%, 3.7%, 3.7%, 3.7%	0%, 4.5%, 4.5%, 4.5%	0%, 4%, 4%, 4%	0%, 0%, 5%, 5%	0%, 0%, 0%, 7%
Power ($n_1=40, n_2=5$)	0.80	0.89	0.80	0.85	0.87
Power ($n_1=40, n_2=3$)	0.79	0.88	0.79	0.83	0.86

Power for different effect size scenarios that give 80%-90% power are presented in the table. If the absolute change in percent time pH < 4 for each of the four diet groups is 3.7%, we will have 80% power to detect any effect of diet. If 1 diet group is not effective and the other groups have a 4.5% effect, we have almost 90% power to detect a diet effect. In our pilot data, the 25th/50th/75th percentiles of percent time pH < 4 were 4.8%/8.5%/12.4%. Thus, a 3.7% decrease is a change from the median to 25th percentile, a 4% decrease is a change from the 75th percentile to the median, a 5% decrease is a change from the 80th percentile to the median, and a 7.6% decrease is a change from the 75th to the 25th percentile. The standard error for any pairwise comparison between groups will be 1.9% under all scenarios ($n_1=40$ and $n_2=3$ or $n_2=5$).

2.3 SPECIFIC AIMS:

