4.0 Inclusion/Exclusion Criteria

As race, age and gender have not been shown to affect GERD status, we will enroll any interested patient who meets the following criteria:

Inclusion Criteria	Exclusion Criteria

 • Age: ≥ 21 years • BMI: 25-45 kg/m² • GERD diagnosis in the medical record which will be confirmed by study baseline pH testing, if baseline pH is not < 4.0 for ≥ 5.5% of time during 24hr testing, subject will be excluded. 	
 • History of type 1 diabetes • Hernia > 5 cm • Current or remote history of esophageal stricture • Gastroparesis • Extra-esophageal GERD • Barrett's esophagus or Esophageal adenocarcinoma • History of gastric or bariatric or esophageal surgery, radiation or cancer • History of gastrointestinal malabsorption • Alcohol averaging > 2 drinks per day during past 3 months • Pregnancy / Lactation

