10.0 Statistical Considerations

Data Analysis: To determine *if percent time with pH < 4 differs by diet treatment group*, we will use multivariable linear regression modeling. Models will include baseline percent time pH < 4.0 and other variables key to disease severity to improve model precision and the diet treatment groups as indicator variables. We will determine *if the primary outcome (% time pH < 4.0) differs by intervention arm*. We will use a linear mixed effects regression model to determine if percent time < pH 4 (Y_{ij}) differs by diet group. The model will incorporate the proportion of time each subject is observed so that subjects that drop out 2 or fewer weeks early are included in the analysis and allowed to have a smaller response to the diet intervention. In particular, for subject i at time j , $Y_{ij} = \bar{Y} + b_i + \bar{X}_{1i} * t_{ij} + \bar{X}_{2i} * t_{ij} + \bar{X}_{3i} * t_{ij} + \bar{X}_{4i} * t_{ij} + e_{ij}$ where $b_i \sim N(0, \sigma^2_b)$ is a subject specific random intercept used to account for repeated observations on the same subject, \bar{Y} is the mean at baseline, X_{pi} are indicator variables for diet group assignment with corresponding effects at 9 weeks \bar{X}_p ($p=1,..,4$), and independent errors $e_{ij} \sim N(0, \sigma^2_e)$. The time the outcome is measured, t_{ij} , is included in the model such that $t_{i1} = 0$ at baseline, $t_{i2} = 1$ for subjects who complete the entire study, and $t_{i2} = p$ for subjects who leave after completing a proportion p of the weeks and come back for final pH testing. Subjects will be included if $p \geq 0.8$.

It is understood that some subjects may drop-out, and thus, not return for the final follow-up visit at week 9, in which case we would have missing values for some response variables. Frequently such dropouts are not a random sample of the entire cohort, and

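### The primary mixed model assumes equal variance at baseline and week 9 although entry cuts only the baseline at 5.5%; between-arm standard errors may be modestly too small, and a fully specified baseline-adjusted analysis removes the risk cheaply

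*Combined protocol and SAP*

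**What the plan says.** Section 10.0 (Data Analysis) describes two analyses of percent time pH < 4. It first says "we will use multivariable linear regression modeling", with baseline percent time, unnamed severity variables and diet indicators. It then sets out a linear mixed model in which baseline and final values are both responses. That model has a "subject specific random intercept used to account for repeated observations on the same subject" and independent errors with one variance. Time is 0 at baseline, 1 for completers and p for early leavers, who are kept if p is at least 0.8.

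Section 4.0 states that "if baseline pH is not < 4.0 for ≥ 5.5% of time during 24hr testing, subject will be excluded". Nothing restricts the final value. Section 5.0 expects 15–20% screen failures from this rule.

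Section 2.2 (Power Analysis and Sample Size) reports that "the SD for percent time < pH was 9.8 and the interclass correlation was 0.39", and that "the 25th/50th/75th percentiles of percent time pH < 4 were 4.8%/8.5%/12.4". It powers a 4 d.f. test of the four diet effects, states absolute effect sizes, and gives a pairwise between-arm standard error of 1.9%.

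**The concern.** A random intercept with a single residual variance implies equal variance at the two visits. Cutting only the first visit from below changes its spread and weakens its correlation with the second. The model then averages the two variances and applies the average to the arm contrasts, whose error is driven mainly by the final value. If the baseline spread is reduced, the average is too small, the intervals are too narrow, and the between-arm test rejects too often. Randomisation keeps the between-arm estimates unbiased; only their stated precision is at risk. Regression with baseline as a covariate conditions on the selected value and does not need equal variances.

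**Working it through.** **Inputs.** Section 2.2: SD 9.8, ICC 0.39, quartiles 4.8/8.5/12.4, two-sided 0.05, and per arm 40 completers plus 5 (or 3) leaving at t = 0.8. Section 4.0: cut at 5.5%. Section 5.0: 15–20% screen failures. The distribution shapes are assumptions, because the plan gives none.

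**1. The plan's own standard error.** Let S be the sum of t² per arm: 40 + 5 × 0.64 = 43.2, or 40 + 3 × 0.64 = 41.92. With common variance V and correlation k, the pairwise SE is √[2V(1 − k²)/S].

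- 9.8 as total SD: √[2 × 96.04 × 0.8479/43.2] = 1.94, and 1.97 with S = 41.92. The plan states 1.9.
- The power table reproduces (all ten entries within 2 points) only if 9.8 is the residual SD, so that the total SD is 9.8/√0.61 = 12.55. The SE is then 2.49–2.52. The plan uses 9.8 in two senses, so both are carried below.

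**2. Effect of the cut.** Let s1 and s2 be the SDs at baseline and follow-up after the cut, and r their correlation. The model uses V = (s1² + s2²)/2 and k = r·s1·s2/V. The actual sampling variance is proportional to s2² + k²s1² − 2k·r·s1·s2.

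- Normal, mean 8.5, SD 9.8: s1 = 6.46, s2 = 9.37, r = 0.27. V = (41.7 + 87.8)/2 = 64.8 and k = 16.3/64.8 = 0.252. The model uses 64.8 × (1 − 0.252²) = 60.6, SE 1.68. The actual value is 82.2, SE 1.95. Ratio 0.86.
- Lognormal, median 8.5, log-SD 0.75: s1 = 10.10, s2 = 10.61, r = 0.32. V = 107.3 and k = 0.320. The model uses 96.3, SE 2.11. The actual value is 101.1, SE 2.16. Ratio 0.98.

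**3. Simulation.** No diet effect, 4,000 trials per row, 45 per arm with 5 at t = 0.8, REML mixed model as written. The last two columns are type I error of the 3 d.f. between-arm test.

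| Shape | SD baseline / follow-up | Model SE ÷ true SE | Mixed model | Baseline-adjusted regression |
|---|---|---|---|---|
| Normal, mean 8.5, SD 9.8 | 6.46 / 9.37 | 0.866 | 12.9% | 5.3% |
| Normal, SD 9.8, 17.5% screen failures | 7.67 / 9.50 | 0.912 | 9.2% | 4.7% |
| Normal, mean 8.5, SD 12.55 | 8.12 / 11.99 | 0.841 | 13.6% | 4.9% |
| Normal, SD 12.55, 17.5% failures | 9.80 / 12.17 | 0.909 | 10.1% | 5.4% |
| Lognormal, median 8.5 | 10.10 / 10.61 | 0.971 | 6.0% | 4.3% |
| Lognormal, 17.5% failures | 9.69 / 10.16 | 0.969 | 6.2% | 4.4% |
| Gamma | 9.53 / 10.32 | 0.962 | 7.3% | 5.1% |
| Lognormal, median 8.5, no cut | 9.74 / 9.77 | 0.975 | 5.3% | 4.6% |

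Monte Carlo error near 5% is √(0.05 × 0.95/4000) = 0.3 points. The skewed rows show shortfalls of 3–4%. A separate run put type I error at about 7% for both skewed shapes, so I quote 3–6%.

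**4. Which shape fits.** A normal with mean 8.5 and SD 9.8 has quartiles 8.5 ± 0.6745 × 9.8 = 1.9 and 15.1, 19% of values below zero (impossible) and 38% below 5.5. The plan's interquartile range is 12.4 − 4.8 = 7.6, against 13.2 for that normal. An SD of 9.8 with so narrow a middle points to a long right tail. The lognormal has quartiles of about 5.1 and 14.1, which is closer though not exact.

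**5. Power.** 43 per arm, lognormal, 3 d.f. test, 2,000 runs per setting, three arms with an effect.

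| Effect in three arms | Mixed model | Regression |
|---|---|---|
| 30/35/40% reduction, with cut | 0.48/0.64/0.79 | 0.61/0.79/0.91 |
| 30/35/40% reduction, no cut | 0.42/0.57/0.75 | 0.59/0.78/0.90 |
| 4/4.5/5 points absolute, with cut | 0.51/0.61/0.69 | 0.48/0.58/0.66 |

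The gap is no smaller without the cut and vanishes with absolute effects.

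**The case against.** The strongest reply is that the large figures need a distribution the plan's own numbers contradict. That stands. In the shape closest to the documents the shortfall is about 3%, and nearly the same without the cut, so most of it reflects skewness and little of it the entry rule.

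A second reply also stands in part: the argument needs the eligibility test to be the t = 0 value. Section 4.0 calls that test the study's baseline pH testing, which favours this reading. Section 6.0, however, puts baseline measures before day 1, tests off PPI on days 7 and 63, and lists baseline and end of week 1 separately. If the day 7 test is t = 0, neither analysed value is directly cut and the variance argument largely disappears.

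Third, a reader might infer that the regression in Section 10.0 is already a correct primary analysis. The text does not support that. Its covariates are open, it names no contrast or degrees of freedom, it has no rule for early leavers, and no power is given for it. The mixed model at least handles early leavers through t = p.

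Fourth, a reader might infer that the plan leaves two rival primary analyses wholly undecided. The Sensitivity Analyses text and Section 2.1 link the primary model to the mixed model, and Section 2.2 powers it. What is missing is an explicit designation.

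**Conclusion.** The equal-variance assumption conflicts with an entry rule that cuts only the baseline, provided the eligibility test is t = 0. Between-arm standard errors are then too small by about 3–6% for right-skewed outcomes (3 d.f. type I error about 6–7%). For normal outcomes, a stress case, the shortfall is about 9–16%, with type I error about 9–13% and 13.6% in the row with SD 12.55 and mean 8.5. These sizes rest on assumed shapes, a correlation of 0.39 before the cut, and 43–45 analysed per arm.

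Two stronger readings are tempting. One is that the standard errors are simply invalid and the analysis must be changed on that ground; the documents' quartiles, SD and expected screen failures do not support the shapes that would make this so. The other is that the cut costs the mixed model power. The gap seen under percentage reductions comes from the assumed proportional effects, and Section 2.2 specifies absolute ones.

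The same cut can also make the planned 4 d.f. test reject through regression to the mean. That is a separate issue and is not counted in this point's severity. The point is a cheap robustness improvement.

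**What to change.** Designate one primary analysis before the data are analysed by arm:

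- (a) linear regression of final percent time pH < 4 on baseline percent time pH < 4, gender stratum and arm, with covariates fixed in advance. Enter three arm indicators against the control diet, each multiplied by t, so that early leavers with p ≥ 0.8 are kept; or
- (b) the two-visit model with a separate variance at each visit and free covariance, keeping the t = p scaling. This removes the constraint by construction; it was not simulated here.

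Use the 3 d.f. between-arm contrast. State which pH test is t = 0. Keep the common-variance random-intercept model as supportive only.

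Restate power for the 3 d.f. test. Using regression on baseline and arm with 45 per arm and the uncut SD, the five scenarios of Section 2.2 give 0.05/0.67/0.55/0.88/0.97 if 9.8 is the total SD, and 0.05/0.44/0.36/0.67/0.84 if it is the residual SD. The first is 0.05 because equal effects in all four arms leave no difference between arms. The two uses of 9.8 must be reconciled first.

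The cost is revised analysis wording and a new power calculation on the same data. The downside is that the stated power becomes less favourable.

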analysis of only the complete cases would bias the results. *We will now request to subjects that inform of us they are dropping out between weeks 7 to 9 that they come in for a final visit. We have found that about 2/3 of subjects will agree to come in for a final visit even if they are not continuing to the end of study (week 9). This will significantly reduce the potential for missing data.* We will also attempt to obtain the specific reason for dropout on a case by case basis. Indirect information about the nonrandom dropouts will be obtained by using binary logistic models to predict the probability of dropping out using baseline variables. Thus, the impact of dropout on our results will be compared using assumptions that vary from missing completely at random to informative missing.

Sensitivity Analyses: We will use the daily diet data and daily medication checklist (type and amount) to conduct secondary analyses and verify the assumptions of our primary model. Summary statistics by diet group will be calculated to determine if weight loss, PPI use, total CHO, and simple CHO are consistent with the study design. We will also use the linear mixed effects model to determine if total and simple CHO are associated with total percent time < pH 4 by replacing the indicator variables in the primary model with these continuous covariates and their interaction. A secondary analysis of changes in PPI use over time will be considered. For this analysis, we will use the diary card data to create continuous variables of the weekly dose of PPI. PPI dose will be the outcome in a linear mixed effects regression model that includes time modeled flexibly using restricted and diet group indicators. An analogous model using weight as the outcome will be estimated. Our study is designed for subjects to maintain weight, but if weight loss differs by treatment arm, it may introduce confounding into our study. We will include weight loss as a covariate in our regression model to determine if our results are altered compared to the main analysis. This additional sensitivity analyses will be conducted as needed, for example where weight change is significantly different among groups, to assure effects are due to dietary not body weight change.

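### The secondary carbohydrate-intake model, built as the plan describes, has no term for a change common to all arms, so a shared change can appear as a carbohydrate association

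*Combined protocol and SAP*

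**What the plan says.** Section 10.0 (Data Analysis) gives one explicit mixed model: a baseline mean, a random subject intercept, and four terms that each multiply an arm indicator by time t. The X variables "are indicator variables for diet group assignment with corresponding effects at 9 weeks". Time is 0 at baseline, 1 at completion, and a proportion p of at least 0.8 for early leavers who return for testing. There is no separate term in t.

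Under Sensitivity Analyses, and again in Section 2.1 (Background PPI Use), the CHO-intake model is obtained "by replacing the indicator variables in the primary model with these continuous covariates and their interaction". The covariates are total and simple CHO. No equation is given. The text does not say whether intake is multiplied by t or entered as a time-varying value, whether it is centred, or in what units. The next model described, for PPI dose, does list time as a term.

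**The concern.** The primary model needs no time main effect because its four indicators sum to 1, so together they carry any change common to all arms. Total CHO, simple CHO and their product do not have that property. If the substitution is followed exactly, the 9-week change is forced to zero at zero CHO intake, which is a regression through the origin. A change shared by all arms, whatever its cause, then has nowhere to go except the CHO coefficients.

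This is the planned model that relates measured intake to acid exposure. A false association, or one with the wrong sign, would feed the discussion in Section 10.0 (Interpretation) of whether simple or total CHO drives reflux and what the next studies should target.

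**Working it through.** **Inputs from Section 2.2.** "We use a two-sided significance level of 0.05"; "the SD for percent time < pH was 9.8 and the interclass correlation was 0.39"; "We assume $n_1=40$ subjects per group complete the entire study and $n_2=5$ or $n_2=3$ subjects per group complete 80% of the study". The diet targets are 55% or 35% of energy as CHO, with 50% or 15% of that CHO simple.

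**1. The plan's own power figures.** I took the Section 10.0 model with a 4-d.f. Wald test and ICC 0.39, and read 9.8 as the residual SD. Power is then 0.815/0.895/0.802/0.859/0.883 for 5 early leavers per arm, against the stated 0.80/0.89/0.80/0.85/0.87. All ten table entries agree within 2 points. Reading 9.8 as the total SD gives 0.96–0.99, which does not match. However, the sentence "The standard error for any pairwise comparison between groups will be 1.9% under all scenarios" fits only the total-SD reading (1.94–1.97, against about 2.5 on the residual-SD reading). Both readings are therefore carried below.

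**2. How closely the CHO terms imitate a shared change.** The arm targets (total T, simple S, in percent of energy) are (55, 27.5), (55, 8.25), (35, 17.5) and (35, 5.25). The least-squares fit of the constant 1 on T, S and T×S without an intercept is 0.02118·T + 0.06101·S − 0.001239·T·S. Its fitted values are 0.97, 1.11, 1.05 and 0.83, so the three CHO terms nearly reproduce a common change.

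**3. Approximate size by hand.** With N = 160 completers, the variance of the mean change is 2σ²ₑ/N.
- Residual-SD reading: 2 × 96.04/160 = 1.20.
- Total-SD reading: σ²ₑ = 0.61 × 96.04 = 58.58, so 2 × 58.58/160 = 0.732.

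If the CHO terms absorb nearly all of a shared change δ, the 3-d.f. noncentrality is about δ²/variance.
- δ = 2: 4/1.20 = 3.3 and 4/0.732 = 5.5, giving rejection of about 30% and 48%.
- δ = 3.7: 13.69/1.20 = 11.4 and 13.69/0.732 = 18.7, giving about 82% and 97%.

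**4. Simulation with no CHO effect.** The basic setting has 40 per arm and ICC 0.39, with assumed within-arm intake SDs of 5 (total) and 4 (simple) percent of energy. Ranges cover both SD readings. They also cover runs with 45 per arm and intake in g/day, with about 2,100 kcal/day assumed for every arm. Entries are 3-d.f. rejection rates without a t main effect.

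| Coding of intake | Shared fall 2 points | Shared fall 3.7 points |
|---|---|---|
| Uncentred × t (literal) | 29–46% (up to 48% in g/day) | 81–97% |
| Time-varying, centred, assumed baseline intake | 14–21% | about 35–57% |
| Mean-centred × t | 6–9% | 9–19% |

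With no shared change, the literal model rejects at about 5%. With a t main effect, every reading returns to about 5% (4–6%). At 3.7 points, the CHO terms absorb about 94% of the fall in the literal g/day model (3.46 of 3.7), and about 11% if intake is centred.

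**5. Direction.** On the literal reading, multiply the step 2 coefficients by −3.7. Total CHO gets −3.7 × 0.02118 = −0.078 and simple CHO gets −3.7 × 0.06101 = −0.226, partly offset by a product term of +0.0046. Both main coefficients say that more CHO goes with a larger fall, against the trial hypothesis.

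On the time-varying reading, assume a baseline of 46.5% of energy as CHO (the GERD subgroup in Table 1), half of it simple as in Section 2.0, so 23.25%. The target mean of simple CHO across arms is (27.5 + 8.25 + 17.5 + 5.25)/4 = 14.6%. A shared fall in acid exposure then coincides with a fall in simple CHO, so the false association favours the hypothesis.

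**6. Is a shared change plausible?** The plan's first power scenario is one: "If the absolute change in percent time pH < 4 for each of the four diet groups is 3.7%, we will have 80% power". Regression to the mean after the 5.5% entry cut is another possible source. It would be roughly 1.7–3.7 points under normality and ICC 0.39, but only if the qualifying recording is also the t = 0 value.

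**The case against.** The strongest reply is that a one-sentence description does not prove the fitted model will lack a time term, and that any statistician would add or centre as needed. The plan does leave the coding open, which is why the table shows three readings and not only the worst. But the instruction is a substitution rule, and following it exactly gives the faulty model. Centring alone does not fully repair it at 3.7 points. The PPI-dose model also shows that the plan names time when it intends it. Section 10.0 mentions a baseline-adjusted linear regression too, whose intercept would absorb a shared change, but the intake analysis names the mixed model.

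A reader might infer several stronger things that the documents do not support.
- *That the trial's answer on simple versus total CHO is invalid.* That answer rests first on the randomised arm contrasts in the primary model, which this fault does not touch.
- *That every shared change is wholly credited to CHO.* The share runs from about 94% to about 11%, depending on coding the plan does not state.
- *That the fault manufactures support for a low-CHO diet.* On the literal reading, the main coefficients point the other way.
- *That the entry cut guarantees a shared fall.* Section 5.0 puts a baseline pH study after consent, while Section 6.0 schedules testing on days 7 and 63. If day 7 is a separate recording and serves as t = 0, the mechanism largely disappears. The normal approximation is also rough: the quartiles 4.8 and 12.4 imply an SD of 7.6/1.349 = 5.6, against the stated 9.8.

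**Conclusion.** The concern holds for the secondary intake model and should be fixed there. It is not a flaw in the primary between-arm comparison. As written, the model has no time main effect, and a change common to all arms inflates the false-positive rate of the CHO test well above 5%. The highest rates belong to the literal reading, and the size and sign both depend on the unstated coding.

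The figures assume no true CHO effect, intakes near the prescribed targets with the stated spreads, and the time-varying baseline given above. The conclusion that t is needed does not depend on those assumptions. How often the fault would matter depends on whether a shared change of about 2 points or more occurs, which the documents make plausible but do not establish.

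**What to change.** In Sections 2.1 and 10.0, write the intake model out in full as baseline mean + random intercept + δ·t + (γ₁·total CHO + γ₂·simple CHO + γ₃·total × simple)·t + error. Alternatively, enter intake as time-varying covariates and add δ·t. State which of the two is used, which diet recalls supply the intake values, and their units. Base the association claim on the CHO terms with t in the model.

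Centring is optional. Once t is fitted, it affects only the interpretation of the main coefficients, and no particular unit is needed for validity. The cost is a line of text, one parameter and slightly less precise CHO coefficients.
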